#### 4.2 STATISTICAL ANALYSIS PLAN

Analysis will be on an intention to treat (ITT) population including all randomized patients, multiple imputation will be used to include participants who have missing outcome data. Comparisons for efficacy will be made between all participants randomised to the different treatment arms, irrespective of whether they received their allocated treatment ("ITT" analyses). Comparisons for safety will be made between all participants randomised to the different treatment arms who have received at least one dose of study medication. Multiple imputation makes a missing at random assumption and a sensitivity analysis around the assumptions made will be performed using controlled multiple imputation that permits exploration of a not missing at random assumption. A complete case analysis will also be performed. The primary outcome will be analysed as binary with participants categorised WHO COVID-19 Ordinal Score <5/  $\ge 5$  by 14 days.

For Stage 1 analysis (after a target recruitment of 171 participants) we will calculate the Wald test statistics from separate logistic regression models for RUX vs SOC and FOS vs SOC, adjusted for stratification variables, with 95% confidence intervals and p-values. P-values will be one-sided and judged at the 0.25 level.

If at least one intervention arm shows promise, then stage 2 will recruit a further 95 per arm (the maximum combined sample size of stages 1 and 2 is 456 patients). The stage 2 analysis will use a one-sided p-value

MATIS version 4.0 dated 2nd November 2022

IRAS: 282552 Page **27** of **57** 

threshold of 0.027. This has been chosen to control the maximum chance of recommending an ineffective treatment at 0.05.

Contamination is a potential threat in many C19 trials, as standard of care is continuously evolving, and coenrolment to ongoing trials present a real challenge if unequal enrolment occurs across arms. For participants who were co-enrolled to a trial at the same time, or prior to the randomisation to this trial, we will adjust the final analysis though covariate adjustment. For participants who were subsequently co-enrolled after randomisation, we treat this as a post-randomisation variable and undertake a supplementary analysis to adjust for this variable along with the receipt of post-randomisation rescue medication.

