In Stage 2 a logistic regression model will be used to assess the treatment effect of RUX and FOS compared to SOC. The model will include the treatment arms, baseline modified WHO Severity Score, trial co-enrolment at baseline, and randomisation stratification variables viz. site and age (<65 vs ≥65). As well as reporting OR and 95% CIs, the model will be used to estimate the difference in proportion of participants with modified WHO COVID-19 Ordinal Score ≥5. The treatment effect in the absence of post-randomisation co-enrolment and receipt of rescue medication will be estimated in a supplementary analysis where participants' outcomes after either will be treated as missing and a controlled multiple imputation using a delta based approach will be used.

For the primary outcome, progression to severe COVID-19 disease within 14 days, discharge alive from the admitting hospital before 14 days will assume safety from the event (in the absence of additional data confirming otherwise). An additional sensitivity analysis will be performed if there is a change of dose after review of the first thirty patients.

For time-to-event analyses required for secondary endpoints such as time to discharge, each treatment group will be compared with SOC and modelled using a proportional hazards time-to-event model adjusted for randomisation stratification variables. Kaplan-Meier estimates for the time to event will also be plotted (with confidence intervals). The log-rank 'observed minus expected' statistic (and its variance) will be used to estimate the average event rate ratio (and its confidence interval) for those allocated to each treatment group versus the no additional treatment group.

Pre-specified subgroup analysis will be conducted for the primary outcome using the statistical test for interaction (or test for trend where appropriate) for the following: disease severity as graded by the WHO

MATIS version 4.0 dated 2nd November 2022

IRAS: 282552 Page **28** of **57** 

Imperial College Healthcare

COVID-19 Ordinal Severity Scale; time since onset of symptoms; sex; age; and comorbidities obesity, chronic heart, lung, kidney and liver disease, diabetes, immunocompromised and smoking status. Pre-specified subgroup analyses will also be conducted for the primary outcome using the statistical test for interaction (or test for trend where appropriate) for patients with admission CRP >200mg/L and/or D-dimer 2500ng/mL.

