# 9.5 LOST TO FOLLOW-UP

The study team will make every reasonable effort to contact participants who have been discharged while on the study to complete the necessary protocol assessments. If any participants are lost to follow-up then the entire data set will be analysed as per the ITT method.

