⁺ data that is routinely collected for clinical purposes will be recorded and a visit is not required

[#] in the event that the patient recovers from COVID19 and is discharged, these visits will not be mandated. Instead a visit should occur on the date of discharge. Where possible, patients will be contacted by telephone at day 7, 14 and 28 and invited to attend for blood tests to monitor resolution of illness.

^{*}Ruxolitinib dose for these patients will be assessed after 10 dialysis patients complete Day 14 through pharmacokinetics (PK) levels which will be assessed.

For patients randomized to ruxolitinib and prescribed a strong CYP3A4 inhibitor or dual CYP3A4/CYP2C9 inhibitor. Please refer to Section 7.8 of study protocol v1.9 for details.

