1.8 Brief description of proposed analysis

Efficacy analysis population: We will use the intention-to-treat (ITT) population which includes all randomised participants analysed in the treatment arm to which they were allocated to regardless of treatment subsequently received, multiple imputation will be used to account for any missing data such that all randomised participants are included in the final analysis. At the formal interim analysis multiple imputation will be undertaken if greater than 5% of outcome data are missing, if \leq 5% missing a complete case analysis will be undertaken.

Safety analysis population: We will include participants who received at least one dose of study medication and analysis will be according to treatment received, regardless of randomised treatment assignment.

The formal interim analysis will be conducted after 171 participants have been recruited and have completed 14 days of follow-up after randomisation. If an experimental treatment is recommended to continue an additional 95 participants will be recruited for each arm that continues and final analysis will be completed after all participants have completed 28 days of follow-up after randomisation.

Formal interim and final analyses will be carried out sub-group blind and follow the ITT principle. That is, all randomised patients will be analysed in the treatment arm to which they were allocated to regardless of treatment subsequently received, multiple imputation will be used to include all randomise participants for the final analysis, at the formal interim analysis multiple imputation will be undertaken if greater than 5% of outcome data are missing. The analysis of the serious adverse events will be undertaken on the safety population.

All regression analysis will include adjustment for age group (<65 years or ≥65 years) and site where appropriate, since these were stratification factors in the randomisation.

All confidence intervals will be presented at the 95% level.

For the formal interim analysis (stage 1) one-sided p-values \leq 0.25 will indicate that an experimental treatment should be recommended to continue to stage 2 and for the final (stage 2) analysis one-sided p-value \leq 0.027 will be interpreted as statistically significant for the primary outcome.

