Every effort will be made to obtain follow-up data for all participants including those that stop treatment. The number and proportion of participants missing WHO COVID-19 status by treatment group and visit will be tabulated (see section 2.5 above). For participants who are discharged early the assumption will be made that they did not progress to grade 5 WHO scale. If there is a >5% rate of missing outcomes after this, we will impute missing WHO COVID-19 data in the primary analysis model using multiple imputation under the assumption of missing at random (MAR). That is the probability of being missing is not dependent on the values of unobserved data, conditional on the observed values of the variables included in the analysis model. Imputation under MAR using chained equations following the guidance of White et al. will be undertaken.⁴ Variables in the imputation model will include the variables in the primary analysis model described above plus baseline WHO COVID-19 score (3 or 4), age (<65 or ≥65), receipt of dexamethasone and/or tociluzimab at the time of or prior to randomisation into MATIS. Additional auxiliary variables that are suspected to be associated with the outcome and are predictors of missingness will also be included. These are receipt of any effective treatments post randomisation as a result of co-enrolment when occurring postrandomisation, and receipt of known effective treatments dexamethasone and tociluzimab postrandomisation (>1 day post randomisation) and WHO COVID-19 scores at day 1 and day 7. Using White et al.'s rule of thumb we will impute m datasets based on the percentage of participants with incomplete outcomes, where m will be rounded to the nearest 10, for example if 8% of participants have incomplete primary outcome then m=10 will be used.

Before undertaking the multiple imputation as described above we will impute any missing baseline data deterministically only using other baseline data, this includes the baseline WHO COVID-19 status, age, receipt of dexamethasone and/or tociluzimab at the time of or prior to randomisation into MATIS. To do this we will impute missing values with the mean values of observed data. In line with White et al., outcomes will be imputed separately for each treatment group.

Imputed datasets will then be analysed using the primary analysis model described above.

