3.2.3 Components of the modified WHO COVID-19 score

The following outcomes will be examined at day 14 and day 28 by replacing the primary outcome in the main analysis model as described in section 3.1.3:

- Death (yes/no)
- Requirement for invasive ventilation plus organ support (yes/no)
- Invasive ventilation (yes/no)

- Non-invasive ventilation including CPAP and high flow nasal oxygen (yes/no)
- Renal replacement therapy (yes/no)
- Venous thromboembolism (yes/no)

Each model will be fitted on complete cases and no imputation of missing values or sensitivity analysis will be undertaken.

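### SAP 3.2.3 analyses death, ventilation, renal replacement and VTE on complete cases with no sensitivity analysis, contrary to SAP 1.8 and protocol 4.2 and 9.5, and states no discharge rule for these outcomes or for day 28

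*SAP*

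**What the plan says.** SAP 3.2.3 analyses six yes/no outcomes at day 14 and day 28 "by replacing the primary outcome in the main analysis model as described in section 3.1.3". These are death, invasive ventilation plus organ support, invasive ventilation, non-invasive ventilation, renal replacement therapy and VTE. It then adds: "Each model will be fitted on complete cases and no imputation of missing values or sensitivity analysis will be undertaken".

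The general rules differ:

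- SAP 1.8: "multiple imputation will be used to account for any missing data such that all randomised participants are included in the final analysis".
- Protocol 4.2: "multiple imputation will be used to include participants who have missing outcome data". It adds a sensitivity analysis under a not-missing-at-random assumption, with a complete-case analysis as a further analysis.
- Protocol 9.5: "If any participants are lost to follow-up then the entire data set will be analysed as per the ITT method".

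Discharged patients have a rule for the primary outcome. SAP 3.1.2 states: "For participants who are discharged early the assumption will be made that they did not progress to grade 5 WHO scale", and assesses missingness only after applying it. Protocol 4.2 states that "discharge alive from the admitting hospital before 14 days will assume safety from the event", in the absence of data showing otherwise.

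On contact after discharge, the footnote to SAP Table 1 (also under protocol Table 7) says: "in the event that the patient recovers from COVID19 and is discharged, these visits will not be mandated". Telephone contact is to be made where possible.

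**The concern.** The same patient can be handled in two ways. A patient discharged on day 8 with no later contact is a non-event in the day-14 composite. In the models for death and ventilation, which are parts of that composite, SAP 3.2.3 does not say whether the patient is event-free or missing. If missing, the patient is dropped. The composite and its components then have different denominators, and the day-28 composite (SAP 3.2.1) uses the imputation model while the day-28 components do not.

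Status to day 28 is known for in-hospital deaths and for patients still in hospital. It is least certain for those sent home, who are mostly survivors. Discharge follows randomisation and is itself an outcome (SAP 3.2.4), so the baseline covariates of SAP 3.1.3 cannot correct for losing these patients. Mortality is the first secondary objective in protocol 2.2, and with sensitivity analyses ruled out, bias in either direction would go unseen.

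**Working it through.** **The plan's own figures.** The documents give none for the component outcomes. The related figures are the 5% missing-data allowance and the power.

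- Evaluable per arm: 54/0.95 = 56.8, so 57 at stage 1; 144/0.95 = 151.6, so 152 in total.
- Stage 1, 50% v 30%, one-sided 0.25, pooled variance, n = 54: (0.2 − 0.6745 × √(0.48/54)) / √(0.46/54) = 1.48, a 93.0% chance of passing (stated 92%).
- Both stages, final one-sided alpha 0.027, correlation √(54/144): 89.4% (stated 90%).

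The sample size reproduces to within about one point, and nothing below affects it.

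**Formula for the bias.** Let p be the true event rate, m the share of event-free patients whose outcome is missing, and e the share of patients with the event whose outcome is missing.

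- Observed odds = true odds × (1 − e)/(1 − m).
- With e = 0: observed rate = p / [p + (1 − p)(1 − m)], and complete-case OR = true OR × (1 − m_SOC)/(1 − m_drug).

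**At the planned 5% missing, all of it among non-events (e = 0).**

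- p = 10%: m = 0.05/0.90 = 0.056; observed rate = 0.10/0.95 = 10.5%.
- Worst split of that 5% over two equal arms, 0% of SOC and 10% of drug: m_drug = 0.10/0.90 = 0.111; observed rates 10.0% v 11.1%; OR factor 1/(1 − 0.111) = 1.125. For true rates of 5% to 15% the factor is 1.12 to 1.13.

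**Larger missingness (assumed; the documents give no values).** True rate 10% in both arms, e = 0:

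| m SOC | m drug | Observed SOC | Observed drug | OR factor |
|---|---|---|---|---|
| 20% | 20% | 12.2% | 12.2% | 1.00 |
| 10% | 20% | 11.0% | 12.2% | 1.125 |
| 20% | 30% | 12.2% | 13.7% | 1.14 |
| 20% | 40% | 12.2% | 15.6% | 1.33 |

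With a real effect of 10% v 6% (OR 0.574) and 20%/40% missing, the data would show 12.2% v 9.6% (OR 0.766). A simulation with a covariate-adjusted logistic model and a true OR of 1 gave 1.01 for 20%/20% and 1.35 for 20%/40%, in line with the algebra.

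**Opposite direction.** If a tenth of the events and none of the non-events were missing (e = 0.10, m = 0), a true 10% would appear as 0.09/0.99 = 9.1%.

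**Scale.** With 152 per arm and an assumed 10% mortality (15.2 deaths), the standard error of the log OR is √[2 × (1/15.2 + 1/136.8)] = 0.38. A factor of 1.125 is 0.12 on the log scale, about a third of one standard error.

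**The case against.** The strongest reply is that few discharged patients need be missing.

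- Protocol 9.1 records vital status, ventilation and dialysis at death, discharge or day 28, and searches notes, routine healthcare systems and registries.
- Protocol section 3 and SAP 1.2 plan weekly telephone follow-up to day 28.
- Protocol 8.5 collects information on all deaths, and protocol 9.5 promises every reasonable effort to reach discharged participants.
- The database items in SAP 3.1.1 ask whether support has been required, which can be answered at discharge.
- A patient assumed not to have reached grade 5 by day 14 cannot logically have died or been ventilated by then. A sympathetic reader could let the primary-outcome rule carry over.

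Most of this stands, and it limits the size of the problem. A reader might infer that missing outcomes will be concentrated in discharged survivors and that a drug that speeds discharge is bound to be penalised. The documents do not support either. None of them states how much will be missing or in whom. Equal shares of missing non-events leave the OR unchanged, and undetected events after discharge push the other way. VTE is not on the protocol 9.1 list at all.

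A reader might also reach an OR of 1.50 by assuming 10% true mortality, 70% v 60% discharged, and every discharged patient missing: 0.10/0.30 = 33.3% v 0.10/0.40 = 25.0%. That would leave 60% to 70% of each arm missing, against a planned 5%, although vital status is recorded at discharge. If 20% of discharged patients are missing, the same model gives 11.6% v 11.4% (OR 1.03).

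The reply does not remove the conflict in the text. SAP 3.2.3 states no carry-over. The logical argument does not reach day 28, renal replacement without ventilation, or VTE. A specific section may override a general one, but SAP 1.8 announces no exception and SAP 3.2.3 gives no reason for one.

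**Conclusion.** The point holds as a conflict and an omission in the text. Complete-case analysis is the only analysis of the component outcomes, sensitivity analysis is ruled out, and the discharge rule is not extended to these outcomes or to day 28.

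The bias is conditional. Rates are overstated if discharged survivors are dropped, and the OR moves against an arm only if a larger share of its non-events is missing. At the planned 5% missing the effect is small: about half a percentage point on a 10% rate, and an OR factor of about 1.12 to 1.13 even if all of it falls in one arm. Anything larger depends on missingness that the documents do not give. These are secondary outcomes; the primary analysis, the 0.027 threshold and the sample size are untouched. The change is still worth making, because it is cheap and the plan currently has no means of detecting the bias.

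**What to change.** Replace the complete-case sentence in SAP 3.2.3 with the following sequence.

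1. Complete the outcomes first from the discharge record, telephone contact and the record sources in protocol 9.1 and 9.2, vital status above all.
2. Count patients discharged alive as free of death, invasive ventilation (with or without organ support) and non-invasive ventilation unless data show otherwise, stated separately for day 14 and day 28. Do not assume this for VTE. For renal replacement, use the dialysis record at discharge and state how the period after discharge is handled.
3. Impute what remains with the multiple imputation of SAP 3.1.2 and 3.1.3, adding discharge status and day of discharge as auxiliary variables where the imputation is stable. Imputation from the analysis covariates alone would essentially reproduce the complete-case result.
4. Report complete-case and best/worst-case (or delta-adjusted) results as sensitivity analyses.

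The cost is SAP wording and some extra programming on imputation code already planned. Imputation by arm may be unstable for rare components, or where discharge almost determines survival; the best/worst-case bounds then carry the sensitivity assessment. Step 2 treats undetected deaths after discharge as survival, which is why step 1 comes first.

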3.2.4 Length of stay

The time to discharge will be summarised by treatment arm using a Kaplan-Meier plot with extended at risk tables, detailing the numbers at risk, censored and discharged at each discrete time point, censoring at the day 28 visit. Withdrawals and deaths will be censored at the date of occurrence. In addition, summaries (means (SD) and median (IQR)) of length of stay will be tabulated amongst those that do not withdraw or die.

In addition, a Cox proportional hazards model will be used to estimate the hazard ratio of time to discharge between intervention arms with age (<65 or ≥65), site and receipt of known effective treatments dexamethasone and/or tociluzimab and vaccination status at the time of or prior to randomisation into MATIS included as covariates.

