# 9 ASSESSMENT AND FOLLOW-UP

# 9.1 COLLECTING FOLLOW-UP INFORMATION

The following information will be ascertained at the time of death or discharge or at 28 days after randomisation (whichever is sooner):

- Vital status (alive / dead, with date and presumed cause of death, if appropriate)
- Hospitalisation status (inpatient / discharged, with date of discharge, if appropriate)
- Use of ventilation (with days of use and type, if appropriate)
- Use of renal dialysis or haemofiltration

This information will be obtained and entered into the web-based IT system by a member of the hospital clinical or research staff. Follow-up information is to be collected on all study participants, irrespective of whether or not they complete the scheduled course of allocated study treatment. Study staff will seek follow-up information through various means including medical staff, reviewing information from medical notes, routine healthcare systems, and registries.

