2.7 Descriptive statistics for outcome measures

The proportion of participants with the primary outcome of WHO COVID- $19 \ge 5$ by day 14 will be summarised by treatment arm and repeated for day 28. This will be undertaken for stage I and stage II.

In addition, the proportion of participants experiencing each of the components of the WHO COVID-19 severity scale score (mortality, invasive ventilation plus organ support (renal replacement therapy, ECMO or inotropic support), invasive ventilation, non-invasive ventilation including CPAP and high flow nasal oxygen) at any point up to day 14 (repeated up to day 28) will be summarised by treatment arm. This will be undertaken for stage I and stage II.

Trajectories of mean (SD) grades over time by treatment arm will also be plotted. This will be undertaken for stage II only.

Time spent at each of the components will be summarised as medians and IQRs by treatment arm. This will be undertaken for stage II only.

All stage 1 analysis of the WHO COVID-19 grades will be completed by the independent statistician in Newcastle University to ensure the trial statistician remains blind and only DMC members will see these results.

Inflammatory markers CRP, LDH, ferritin, D-dimer, and serum creatinine values will be summarised by treatment arm over time and presented as means (SD) and median (IQR). This will be undertaken for stage II

Summaries (means (SD) and median (IQR)) of length of stay will be tabulated amongst those that do not withdraw or die. This will be undertaken for stage II

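### Kaplan-Meier plot of time to discharge censors deaths, so any proportion discharged read from it is too high; no cumulative incidence of discharge is planned

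*SAP*

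**What the plan says.** SAP 3.2.4 (Length of stay) plans three things for this outcome.

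- A Kaplan-Meier plot of time to discharge by arm, with a table under it "detailing the numbers at risk, censored and discharged at each discrete time point" and follow-up ending at the day 28 visit. For this plot, "Withdrawals and deaths will be censored at the date of occurrence". Deaths have no column of their own in the table.
- Means and medians "of length of stay will be tabulated amongst those that do not withdraw or die". SAP 2.7 plans the same summary.
- A regression: "a Cox proportional hazards model will be used to estimate the hazard ratio of time to discharge between intervention arms". This comes shortly after the censoring rule, in the same subsection and for the same outcome.

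Protocol 4.2 covers time-to-event secondary endpoints and gives time to discharge as its example. It plans a proportional hazards model, Kaplan-Meier curves, and a log-rank "statistic (and its variance) will be used to estimate the average event rate ratio". It does not say how deaths are handled.

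Neither document plans a cumulative incidence or other competing-risk summary of discharge. The mean cumulative function plots in SAP 2.8 are for recurrent adverse events. Death is summarised by arm in SAP 2.7 and modelled separately at days 14 and 28 in SAP 3.2.3.

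**The concern.** Kaplan-Meier treats a censored patient as someone who could still have the event later, at the same rate as those who remain at risk. That is reasonable for a withdrawal but wrong for a death in hospital. Censoring the death passes that patient's weight to those still in hospital, as if the patient would eventually have gone home. The complement of the curve therefore exceeds the real proportion discharged alive.

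Reducing the duration of admission is a stated efficacy objective (Protocol 2.2), so readers will look at this figure. Two things are at stake: the level read from the curve in each arm and, if mortality differs between arms, how the arms compare. Survivor-only stay has a related weakness. If sicker patients both stay longer and die more often, an arm with more deaths loses its longest stays from the average.

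**Working it through.** The documents state no discharge, stay or mortality figure, so there is nothing of theirs to reproduce. Every rate below is an assumption.

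**Step 1: the excess in one arm, in closed form.** Let the discharge hazard be d and the in-hospital death hazard be m, both constant over 28 days.

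- True proportion discharged alive: d/(d+m) × (1 − exp(−28(d+m))).
- Read from Kaplan-Meier with deaths censored: 1 − exp(−28d).

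If D is the proportion discharged alive and M the proportion dead by day 28, the Kaplan-Meier reading is 1 − (1−D−M)^(D/(D+M)). For D = 0.80 and M = 0.10 this is 1 − 0.10^(0.889) = 0.871, which is 7.1 points too high.

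| True discharged | 2% deaths | 5% deaths | 10% deaths | 15% deaths |
|---|---|---|---|---|
| 70% | 71.0% | 72.6% | 75.5% | 79.0% |
| 80% | 81.2% | 83.2% | 87.1% | 92.0% |
| 85% | 86.4% | 88.6% | 93.1% | not possible |

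The excess runs from 1.0 to 12.0 points.

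**Step 2: the same, with sicker patients staying longer and dying more.** Severity U is standard normal. Discharge time is exponential with mean 9·exp(0.8U) days. Time to death in hospital is exponential with mean B·exp(−1.2U) days, and B sets mortality. Simulation of 500,000 patients per arm to day 28 gives:

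| Deaths (B) | Kaplan-Meier | True | Excess |
|---|---|---|---|
| 2% (1,500) | 89.3% | 88.0% | 1.3 |
| 6% (450) | 90.1% | 86.3% | 3.8 |
| 9% (260) | 90.6% | 84.5% | 6.1 |
| 16% (110) | 92.0% | 79.8% | 12.2 |

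The median from Kaplan-Meier against the true curve is 5.8 against 5.9 days at 6% deaths, and 5.6 against 6.1 at 16%. Under step 1 the largest gap in medians is 1.4 days (12.4 against 13.8, at 70% discharged and 15% deaths).

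**Step 3: between arms, with no drug effect on speed of discharge.**

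- Constant discharge hazard of 0.08 per day, with only mortality varied (0%, 4.3%, 8.3%, 15.5%). Kaplan-Meier reads 89.4% each time, while the true proportion is 89.4%, 86.2%, 83.2% and 77.7%. The plot hides the difference.
- Severity model, control deaths 16%, death hazard 1.5 times higher on the drug (about 20% deaths). Kaplan-Meier reads 92.0% against 92.9%; the truth is 79.8% against 76.6%. The order reverses, but by 0.9 points on the plot.
- The same 1.5-fold hazard at lower control mortality: 90.6% against 91.2% (9% deaths) and 90.1% against 90.4% (6% deaths). The reversals are 0.6 and 0.3 points.
- Equal mortality: no between-arm difference arises.

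**Step 4: survivor-only stay.** In the 16% against 20% case, mean stay excluding deaths is 7.3 against 6.7 days if patients still in hospital at day 28 count as 28 days. Among those actually discharged it is 6.2 against 5.9 days. The SAP does not say which convention applies.

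**Step 5: the Cox ratio with deaths censored.** In the severity model at 16% control deaths it is 1.02 when the drug's death hazard is multiplied by 1.5, and 0.96 when multiplied by 0.4. The true ratio for speed of discharge is 1.00.

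**The case against.** The SAP does not say that a day-28 proportion or a median will be taken from the curve. The planned numerical summaries are the tabulated means and medians and the Cox ratio, and the numbers discharged are printed under the plot. Survivor-only stay carries no test and is clearly labelled, and mortality is reported by arm. All of this is true, and it limits the harm. It does not remove the point: a plot of time to discharge is normally read as the proportion discharged, and the table pools deaths with withdrawals as censored.

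A reader might infer that the SAP's Cox model fails to handle deaths or is biased by censoring them. The documents do not support this. The censoring sentence precedes the Cox sentence in the same subsection and naturally covers it. With deaths censored, the model compares discharge rates among patients still alive in hospital, with all randomised patients entering it. That is a legitimate cause-specific comparison. Only Protocol 4.2 is silent on deaths.

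A reader might also infer that the arms are likely to be ranked wrongly. That needs a real mortality difference, and even then the plot's reversal is under 1 point at a 1.5-fold death hazard. With 152 per arm, in the 16% against 20% case, survivor-only stay was shorter on the drug in 71% of simulated trials. That counts only the sign, which is 49% at equal mortality; the difference was nominally significant in about 9%.

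**Conclusion.** The point holds for the plot. Whenever anyone dies before discharge, the Kaplan-Meier curve as specified overstates the proportion discharged in that arm; this direction needs no assumption about rates. The size does: about 1 point at 2% deaths, 4 at 6%, 6 at 9% and 12 at 16% under the severity model, with 1 to 12 points in the closed-form check. The median is little affected.

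Between arms, distortion arises only if mortality differs. The plot may then hide or slightly reverse a difference in live discharge, and survivor-only stay reflects deaths as well as recovery. The Cox ratio stands as a cause-specific measure, but it does not give the probability of going home. This is a secondary outcome with mortality analysed separately, so the primary conclusion, sample size and error rates are untouched. It is a worthwhile reporting correction, not a threat to the trial.

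**What to change.** In SAP 3.2.4:

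- State that death in hospital is a competing event for discharge alive. Plot the cumulative incidence of discharge alive and of death in hospital by arm to day 28, with withdrawals censored.
- Take any reported proportion discharged or median time to discharge from that plot.
- Keep the Kaplan-Meier plot alongside to meet Protocol 4.2, captioned as not giving the proportion discharged. Give deaths and withdrawals separate columns in the table beneath it.
- Say explicitly that the Cox model and the log-rank rate ratio censor deaths at the date of death, and label both as cause-specific.
- Present survivor-only stay next to day-28 deaths by arm, and state how patients still in hospital at day 28 are counted.

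The cost is some SAP wording, a few lines of code and one more figure. Protocol 9.1 already collects dates of death and discharge, so no new data are needed. The downside is two discharge curves per arm, which need a clear caption to keep them distinct.
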